The StepRite system developed by MedHab (<http://www.medhab.com/>) allows the physical therapist to monitor physical activity and exercise remotely, thereby reducing the need for frequent out-patient visits. A thin insole placed inside the shoe measures foot contact pressure and acceleration. This information is translated into quantitative feedback about exercise compliance and performance measures comparing the surgical side with the non-surgical side. Real time feedback during exercise and weight-bearing activities is

provided to the patient, and a HIPAA secured user interface website also displays this information in an online dashboard for both physical therapists and the physician.

With the advent of federally mandated bundled payments for total joint replacement, active management of the rehabilitative process postoperatively with quantifiable data will be necessary to ensure financial stability.

Given the potential for improving patient engagement with rehabilitation, this study proposes a treatment model which includes monitoring activity outside of the clinic using the StepRite device and using a combination of outpatient appointments and remote consultations with therapists.

Significance of this study

The significance of the proposed study includes the projected benefit to the patients in terms of attaining clinical outcomes quicker and to the medical system in terms of managing cost for the provision of services. Subjects are expected to demonstrate improved compliance to patient tailored rehabilitation protocols which will lead to more rapid attainment of clinical outcomes versus present traditional rehabilitation methodologies. The expected level of, and rate of, attainment of clinical outcomes will translate to an overall reduction of cost to the medical system by reducing the need to engage in additional processes or the need to protract the time required to attain clinical outcomes, where either or both in combination can increase rehabilitation expenditures.

Objectives

To compare the efficacy of StepRite in a prescribed physical therapy program verses traditional in-facility physical therapy program after partial or primary total knee replacement using validated survey tools to evaluate patient progress, including patient self-reporting of progress and surgeon appraisal of patient performance post-operatively.

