To compare the overall cost of post-operative rehabilitation of patients involved in traditionally employed regimens versus those using the StepRite device.

Hypothesis and specific aims

The aim of this study is to evaluate whether improved clinical outcomes as well as reduction in cost in provision of care can be better affected through the use of the Steprite device as compared to the use of traditional rehabilitation modalities.

We will seek to reject the null hypotheses that 1) there is no difference between clinical outcomes attained between patients using the Steprite device and those using traditional rehabilitation modalities and that 2) there is no reduction in cost to the medical system when patients use Steprite versus other conventional methods of rehabilitation.

By rejecting the null hypothesis we will accept the alternate hypothesis that, through the use of the Steprite device, not only will patients achieve overall clinical outcomes faster but there will be an associated decrease in cost burden to the medical system and the differences observed will be statistically significant as compared to rehabilitation of patients not using the Steprite device.

Patients who use the device post-surgery will demonstrate superior short-term improvements (i.e. 3 months post-surgery) with respect to self-reported functional outcomes and gait parameters, compared to a control group not using the device. The patients will self-report through the use of validated survey instruments including the KOOS survey (knee injury and osteoarthritis outcome score), LEFS (lower extremity functional scale) and/or KSS (knee society score), the latter of which includes a section for surgeon evaluation of patient functionality post operatively.

Study Design and Methods

This is a point of care clinical trial; a trial that functions to integrate research within a clinical setting that has the ability to readily deliver either modality of the proposal. This type of study design relies on provider referral of patients to be approached for consent, after which randomization to one of two treatment groups is facilitated; a control group of 15 patients participating in conventional rehabilitation regimens and an experimental group of 15 patients who will participate in the same rehabilitation regimen but facilitated

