through the use of Steprite. Importantly, care for patients is delivered as part of current adopted standards utilizing outcome measurements, the use of which and the interpretation of which is already built into care provided by the clinical facility, thereby negating the need to develop additional outcome measures. Recruitment of 30 patients will come from the investigators' normal patient population, among patients who are scheduled for partial or total knee arthroplasty. As there is no change in post op care for these patients from the investigators standard protocols other than monitoring and enforcement of home protocols, the same therapists involved in investigators' normal patient care will be involved with both arms of the study.

For this study, 30 patients represents a sample size deemed acceptable as a starting point. There are no other published studies using Steprite in comparative design trials. Determinations of sample size needed for this study, using 80% power and significance of 0.05, incorporate the use of a time frame in days or weeks for completion of the rehabilitation protocols that would allow for the detection of clinically significant differences between the group using Steprite and those using conventional therapies only. Given that conventional therapies can include skilled nursing, home health and outpatient visits and given that the need for each of these is highly variable dependent on the patient, it is difficult to assign a time value for determinations of sample size.

With that, a sample size of 30 participants divided into two groups represents an initial starting point, with the potential of incremental addition of more patients in order to achieve significance between the two study groups.

Statistical significance will be evaluated utilizing a standard t-test for two group comparison.

In preparation for the study, MedHab Inc. will at their expense train all involved investigators and therapists in the fitting and use of the StepRite device. Medhab will also train a lead therapist designated by the lead investigator to be in charge of overseeing and monitoring, ensuring proper use of the device. There is no cost to the patient, hospital or other funding entity for participation in this study. Medhab LLC will assume all costs associated with the training, application, device and use of the StepRite product for the full course of this study.

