There is a risk of loss of confidentiality, we will have measures in place to help prevent any loss of personal information. During the course of this study there are no new or additional steps required of the subjects from what is considered the standard protocol for the lead investigator. The only alteration may be reduced travel and outpatient visit by the patient if compliance and functional improvement noted by the therapist. StepRite imparts no energy to the patient and poses no hazard to patient well being. Subjects will be free to withdraw from the study at any time and revert to conventional rehabilitation treatment.

Possible benefits to subjects

There is a possibility the device group patient could benefit from the device prompting them to do their own exercises regularly, which could lead to a faster recovery and better physical therapy outcomes. We are hoping the participation in this study may help us learn how we can design rehabilitation programs to be more effective in the future.

Confidentiality measures

StepRite / MedHab will have access to non-PHI patient data collected by the device stored on their HIPPA compliant server and be available only to the lead investigator. All PHI will be kept separate from the study data in a locked filing cabinet or on a password protected computer in the research coordinators office in 4A144B.

Data Collection and Monitoring

Data recorded by the StepRite device will be transmitted wirelessly to the HIPAA secured web interface managed by Medhab. Clinicians will be able to log into the website with a password to review the progress of each patient.

Data recorded by the PI and physical therapist on the functional motion of the knee will be recorded in paper form and kept with the completed KOOS questionnaire and Knee Society Score (KSS) and scanned into the patients HIPPA protected chart.

Upon completion of patient's part in the study MedHab will contact UMC and the Therapy departments to acquire actual costs of these services. This will be done to compare the overall cost of management of the post-operative rehabilitation of a patient in traditional rehabilitative regimen vs. use of StepRite,

Actual Cost information for the patient's full rehabilitation will be requested and collected by the Hospital and released to MedHab at the end of the study and supplied to the lead investigator for analysis.

References

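### The cost comparison, by inference, covers rehabilitation services without the StepRite device, so it does not by itself support a conclusion about cost to the medical system where StepRite must be paid for

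*Combined protocol and SAP*

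**What the plan says.** Cost is the subject of one of the two null hypotheses. Under Hypothesis and specific aims, the second null is that "there is no reduction in cost to the medical system when patients use Steprite versus other conventional methods of rehabilitation". On rejection, the planned conclusion is that "there will be an associated decrease in cost burden to the medical system and the differences observed will be statistically significant".

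Under Study Design and Methods, MedHab will "assume all costs associated with the training, application, device and use of the StepRite product for the full course of this study". The sentence before it says that neither patient, hospital nor any other funder pays for participation.

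Under Data Collection and Monitoring, "MedHab will contact UMC and the Therapy departments to acquire actual costs of these services". The same section says that cost information for the patient's "full rehabilitation will be requested and collected by the Hospital", released to MedHab, and passed to the lead investigator for analysis. There is no list of cost components, no price for StepRite and no stated costing perspective.

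The motivation looks beyond the trial. Background opens its case on payment "With the advent of federally mandated bundled payments for total joint replacement", and Significance of this study expects that better attainment of outcomes "will translate to an overall reduction of cost to the medical system".

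**The concern.** StepRite patients receive conventional care plus a device (Schedule of events). Under Risks, the change in care that the protocol foresees is this: "The only alteration may be reduced travel and outpatient visit by the patient". Fewer outpatient visits would appear in the therapy departments' costs. The cost of the device, app and training that produced the reduction would not, because MedHab absorbs it and MedHab's outlay is not among the named data sources. The comparison would credit StepRite with visits avoided without charging it for the device.

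A significant difference would then show lower rehabilitation service cost when the device is supplied free. The planned conclusion is worded more broadly. A hospital or payer working under a bundled payment could read it as a net saving, although in routine use someone would have to buy the device. If the price exceeded the service saving, net cost would rise while the planned comparison still favoured StepRite.

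**Working it through.** **Step 1: what the cost data can contain.**

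| Item | Protocol section | Content |
|---|---|---|
| Target of the conclusion | Hypothesis and specific aims | Cost to the medical system |
| Data sources | Data Collection and Monitoring | UMC and the therapy departments |
| Payer for device, app, training and use | Study Design and Methods | MedHab, throughout |
| StepRite price | None | Not given |
| Rule adding or excluding a price | None | Not given |

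The named sources report their own actual costs, and they pay nothing for StepRite. Their figures should therefore hold no device cost. This is an inference from the sources and the funding rule; no section says that the device is left out.

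**Step 2: effect of a device cost.** Let C and T be the mean service cost per patient in the control and StepRite arms, and D a constant StepRite cost per patient.

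- Service saving: S = C − T.
- Net saving: C − (T + D) = S − D.

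A constant leaves the SD unchanged, so the whole confidence interval moves down by D. If L is the lower 95% limit for S, net saving is zero at D = S, and the saving stays significant at two-sided 0.05 only while D is below L. With complete service costs, the overstatement from the wider perspective is exactly D.

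**Step 3: size.** The protocol has no cost figure to reproduce: no price, expected saving, cost per visit or cost SD. The rest is illustration only. It assumes normal costs, equal SDs, 15 per arm as planned, the planned t-test, and two-sided 0.05 (the protocol gives 0.05 without saying one- or two-sided).

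- Critical value on 28 degrees of freedom: 2.048.
- Smallest significant difference: 2.048 × √(2/15) = 0.748 SD.
- For an observed service saving of 1.0 SD, the break-even price is 1.0 SD. The highest price at which it stays significant is 1.0 − 0.748 = 0.25 SD.

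Now suppose the true net saving is zero, so that the true service saving equals D. The chance that the device-excluded test declares a saving is the upper tail of a noncentral t beyond 2.048, with noncentrality (D/SD) × √(15/2):

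| Assumed D/SD | 0 | 0.1 | 0.25 | 0.5 | 1.0 |
|---|---|---|---|---|---|
| Chance of declaring a saving | 2.5% | 4.5% | 9.7% | 26.2% | 75.3% |

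These figures are also the test's ordinary power to detect a real service saving of D. They count as errors only if the conclusion is read as covering the cost of the device.

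**Step 4: scale in visits.** The control outpatient schedule is twice weekly to 8 weeks: 2 × 8 = 16 visits. If D equals the cost of k visits and only outpatient visits differ, the first k visits avoided merely pay for the device: 2/16 = 12.5%, 4/16 = 25% or 8/16 = 50% of the schedule for assumed k of 2, 4 or 8. Some patients will also have other forms of care, so this scale is rough.

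**The case against.** The best defence is that service cost is what the plan means. The cost objective is the cost of post-operative rehabilitation, the stated aim speaks of the cost of providing care, and Significance of this study frames the system's benefit as managing the cost of providing services. The sentence there that predicts an overall reduction goes on to explain it by less need for extra or prolonged rehabilitation. Inside the trial the device is free, so service cost is the system's outlay. This much stands: the measure is valid for the trial as run, and the narrower reading is compatible with the text. It does not settle the matter, because the planned conclusion is not confined to that reading and Background places the device in a payment setting outside the trial.

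A second defence is that the exclusion rests on silence. Data Collection and Monitoring describes the comparison as one of overall management cost, and the data pass through MedHab, which knows what it spends. A device cost could therefore be added. That is true, but the plan gives no value and does not say that it will be done.

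The Device Flow Chart also lists an assignment-of-benefits form for patients to sign, which might suggest that a payer is billed. The documents do not explain it. It sits uneasily with the no-cost statement and brings no price into the comparison.

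Finally, every D/SD and k value above is assumed. Because the protocol calls the need for each type of care highly variable, the cost SD may be large and the low end of the table may apply. The illustration shows the mechanism, not the harm.

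**Conclusion.** The point holds as a mismatch between what the cost data can show and how the conclusion is worded. Following the named sources and the funding rule gives rehabilitation service cost excluding StepRite. A significant result would support lower service cost with a free device; it would not by itself establish a reduced burden on the medical system where the device is bought. From that wider perspective the overstatement is D per patient, assuming service costs are otherwise complete. Its size in dollars cannot be determined from the documents.

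A reader might infer more: that the cost analysis is invalid, that the plan sets out to exclude the device, or that any saving found would be spurious. The documents support none of these. The in-trial measure is sound, no passage excludes a device cost, and without a price nobody can say whether a service saving would survive it.

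**What to change.** Amend Hypothesis and specific aims and Data Collection and Monitoring before any cost data are released.

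1. State that the tested cost outcome is rehabilitation service cost excluding StepRite, and limit hypothesis 2 and its conclusion to that.
2. Report the difference (control minus StepRite) with its 95% CI. Present the point estimate as the break-even StepRite price per patient, and the lower limit as the highest price at which the saving stays significant at two-sided 0.05. If the lower limit is zero or below, no price qualifies.

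If the sponsor prefers to keep the medical-system conclusion, it should instead fix in advance one base-case StepRite cost per patient (device, app and a share of training) and add it to every StepRite patient in the tested outcome. A range of prices should serve only as sensitivity analysis, because testing across a range gives no single result for hypothesis 2.

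The first route costs a paragraph of definition; the second also needs one costed figure, presumably from MedHab. Neither needs extra visits or patient data. The price of the change is a narrower conclusion under the first route, or a smaller claimed saving under the second. Writing it down beforehand keeps the perspective from being chosen once the result is known.

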Subjects for this study will be recruited from the patient population seen by the investigators during the normal course of business. There will be no outside recruitment of individuals or advertising as to the presence or use of the monitoring device to entice new patient referral. Prospective candidates will be asked by the lead investigator at the time they are designated surgical candidates. All documentation related to the study will be reviewed with the patient by the lead physician or his designee who is appropriately trained in discussing patient recruitment. Final decision and randomization to control or StepRite use will be done as part of the preoperative checkup just prior to surgery where both operative consent and study consent are discussed and signed.

Randomization:

Once a patient agrees to the study they would be sequentially randomized into whether or not they receive StepRite. The patients will be randomized to every other eligible patient gets the intervention. (ie: 1,3,5,7,9... will get StepRite ; 2,4,6,8 will not get StepRite) 15 Intervention subjects will be recruited and 15 control subjects will be recruited with an extra 5 patients to account for attrition and withdrawals.

Schedule of events

The intervention group will receive the StepRite device with standard conventional care and the control group will receive standard conventional care only. Both groups will receive outpatient, home health, and /or 24 hour physical therapy treatment plans per their surgeon's standard of care. The control group will undergo the conventional outpatient treatment program to 8 weeks as normally prescribed by the lead investigator. This consists of a twice weekly outpatient appointment with a physical therapist and prescribed home exercise program (see attached physical therapy protocol).

The patients randomly selected to wear the StepRite inserts will be fitted and instructed along with the patient's designated care giver in their use including initial pre-op measurements prior to their surgical date so that data collection can begin on the 1st day of rehab after surgery

Those patients not selected to wear step rite will receive instructions preoperatively of their expected therapy regimen and receive their baseline functional evaluation of the knee

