Both groups will be given log sheets to record their activity at home and when seen by the physical therapist. These will be returned and collected by the therapist weekly and scanned into/ kept in the patient's medical record file. A paper copy will be kept in the coordinator's office, 4A144B with the consent forms and any other study documents.

Both groups will also have routine self-assessment questionnaires (appendices 3, 4 KOOS and KSS) and functional testing performed by the PI and PT during the patient's regular clinic visit as standard of care.

Outcome measurements performed just after surgery and at time of discharge from hospital and standard of care post-surgical clinic visits to 8 weeks will indicate if any patients are experiencing unexpected delays in progress. Subjects will be visited at home by the Home Health therapists, and will visit and receive telephone consultations with the outpatient therapists, who will be able to monitor the patients' conditions and intervene if there are any problems related to the use of the device. The StepRite device will provide the therapist with more information about the patients' activity levels and progress than would usually be available to them and so is not expected to have any safety implications. The device and App. will prompt the patient with voice and text to complete their exercises as they are needed, while collecting data.

Device Flow Chart: standard of care post-op

The research coordinator will consent the patient prior to the surgery

The research coordinator will document the following information for the device on the device data collection form. (See attached)

- a. Name of patient
- b. Email of patient
- c. Phone number of patient
- d. Surgery date
- e. Expected date of discharge

The patient's information will then be entered into the steprite™ system and a patient account will be created by the Research Coordinator

Physical therapy will schedule the study protocol via the steprite™ system and enter the physical therapy start date as day after discharge.

MedHab™ sponsor ([name]) will contact the patient for the patient account set up and to obtain the following signatures required by MedHab (see attached)

- a. HIPAA
- b. Assignment of Benefits

MedHab™ will help the patient load the app, provide an overview of the app, and forward a tutorial video
MedHab™ will send the steprite™ device to the study Research Coordinator at TTUHSC

TTUHSC Orthopaedic Surgery

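### Allocation is strict odd/even alternation labelled as randomization, with no concealment, so those who recruit can know the next arm before they approach a patient

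*Combined protocol and SAP*

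**What the plan says.** The Randomization section of the combined protocol and SAP sets the rule: "The patients will be randomized to every other eligible patient gets the intervention". It then gives the sequence: "ie: 1,3,5,7,9... will get StepRite ; 2,4,6,8 will not get StepRite". The same section opens with "Once a patient agrees to the study they would be sequentially randomized into whether or not they receive StepRite".

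Other sections describe how patients reach that point:

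- **Referral.** Study Design and Methods states: "This type of study design relies on provider referral of patients to be approached for consent, after which randomization to one of two treatment groups".
- **Approach.** The recruitment text just before the Randomization section says: "Prospective candidates will be asked by the lead investigator at the time they are designated surgical candidates".
- **Timing.** The same text says: "Final decision and randomization to control or StepRite use will be done as part of the preoperative checkup just prior to surgery". Study consent is discussed and signed at that visit.
- **Eligibility.** Under the heading on identifying and recruiting subjects, the investigators pick out patients and consult the research coordinator on eligibility.
- **Consent.** The Device Flow Chart says: "The research coordinator will consent the patient prior to the surgery".

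The analysis is a standard two-group t-test, with no baseline adjustment mentioned. Schedule of events still refers to random selection of the StepRite patients. The document nowhere describes a generated sequence, concealment, an independent assigner or masking.

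**The concern.** A two-group t-test, and a causal reading of its result, need groups that differ at baseline only by chance. Random allocation gives that assurance only if the next assignment cannot be foreseen by those who decide who enters and when. Alternation fails on both counts: it contains no chance, and anyone who knows the last patient's arm knows the next one.

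The device cannot be hidden, so the last patient's arm is visible. A recruiter who expects StepRite to work can, without intending to, approach a motivated patient when the next slot is odd and wait when it is even. Patients may have partial or total knee replacement, and no stratification is planned, so procedure type is one obvious characteristic on which the arms could drift apart. A patient can also be deferred, or can decline, once the arm is known.

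The stakes are high because Hypothesis and specific aims reads rejection of the null as showing faster recovery and lower cost with StepRite. The planned t-test cannot separate a difference created by selection from a device effect.

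**Working it through.** **1. Is there any chance element?** The odd/even rule gives 15/15 for 30 patients, which reproduces the planned split, and 18/17 for the 35 requested. Each assignment, including the first (StepRite), has probability 1 given its place in the sequence.

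**2. Does allocating after agreement protect the comparison?** No. The arm attached to the next place is fixed before anyone is approached. The wording also leaves the counting unit unclear: "The patients will be randomized to every other eligible patient gets the intervention" counts eligible patients, while "Once a patient agrees to the study they would be sequentially randomized into whether or not they receive StepRite" counts those who agree. That leaves room to reorder patients.

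**3. How predictable is each scheme?** The recruiter is assumed to see all past assignments and to guess the arm that is behind, or to toss a coin when the arms are level. Simulated over 30 patients (5,000 runs for the two random schemes):

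| Scheme | Next arm guessed correctly |
|---|---|
| Alternation (as planned) | 100% |
| Permuted blocks of 4 and 6 | about 69% |
| Simple randomization | about 50% |

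**4. What could steering do to the t-test?** Inputs from the protocol: 15 per arm, significance level 0.05, two-group t-test. Sidedness is not stated, so two-sided is assumed. The prognostic shift η is an assumption with no source in the documents.

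Model: no true device effect and unit SD within each arm. Patients entering StepRite slots have mean prognosis +η, and those entering control slots have −η.

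- Spurious difference: d = η − (−η) = 2η.
- Noncentrality: d × √(15/2) = 2.739 × d, with 15 + 15 − 2 = 28 degrees of freedom.
- False-positive rate: the probability that this noncentral t falls outside the central two-sided 5% limits.

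| η (SD, assumed) | d = 2η | Noncentrality | False-positive rate, alternation |
|---|---|---|---|
| 0 | 0 | 0 | 5% |
| 0.10 | 0.20 | 0.548 | 8.3% |
| 0.15 | 0.30 | 0.822 | 12.5% |
| 0.20 | 0.40 | 1.095 | 18.5% |
| 0.25 | 0.50 | 1.369 | 26.2% |
| 0.50 | 1.00 | 2.739 | 75.3% |

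If only a fraction f of patients is steered, the spurious difference is 2fη. A 0.25 SD shift in 40% of patients gives 2 × 0.4 × 0.25 = 0.20, the same difference as the η = 0.10 row.

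**5. What would the alternatives give?** With a sequence that cannot be guessed, the same steering leaves bias near 0 and a false-positive rate near 5% at every η (4,000 runs each). With blocks of 4 and 6 and the guessing strategy in step 3 (3,000 runs each):

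| η (SD, assumed) | Mean bias (SD), blocks | False-positive rate, blocks | False-positive rate, alternation |
|---|---|---|---|
| 0.10 | 0.07 | 5.5% | 8.3% |
| 0.20 | 0.15 | 6.7% | 18.5% |
| 0.25 | 0.18 | 6.6% | 26.2% |
| 0.50 | 0.37 | 14.7% | 75.3% |

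The block rates carry simulation error of about half a percentage point near 7%, which explains why 6.7% and 6.6% are out of order.

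**The case against.** The strongest reply is that the rule permits steering but does not show that it will happen.

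- **Who knows the next arm.** Patients are asked when they become surgical candidates but are assigned later, at the preoperative checkup, and others may agree or decline in between. Several investigators may refer, and the coordinator takes consent. This stands in part: the text supports that recruiters can know the next arm, not that a given surgeon always does. In one department enrolling 30 to 35 patients, however, the running count is easy to learn.
- **Size.** The shifts are assumptions, and the model steers every patient in the same direction. This stands, so the error rates are illustrations and not estimates for this trial.
- **Baseline data.** Preoperative measurements are taken, and procedure type is known, so some imbalance could be seen and adjusted for. This stands for measured factors, although no adjustment is planned. Motivation and similar traits would remain unmeasured.
- **Phone skill.** All participants must own and know how to use a smartphone, which narrows the scope for steering on that trait. This stands.
- **The remedy is imperfect.** In an open trial, blocks remain partly guessable, at about 69% for sizes 4 and 6. This stands, but it is a clear improvement on 100%.

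None of these points supplies a random sequence or concealment.

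**Conclusion.** The concern holds. The protocol claims a randomized comparison that its stated rule does not deliver. All assignments are determined by enrolment order, nothing conceals them, and those who refer, approach and screen patients can know the next arm before consent. That much follows from the text alone.

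The size of any resulting bias is unknown. The illustrated false-positive rates of 8.3% to 26.2% rest on assumed shifts of 0.10 to 0.25 SD applied to all patients in one direction, a two-sided test and 15 per arm. The change is needed before the first patient is enrolled, because no later analysis can fully separate selection on unmeasured prognosis from a device effect.

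**What to change.** Replace the odd/even rule, and delete the numbered example, with text to this effect:

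- A computer-generated 1:1 list in permuted blocks of randomly varying size, with the sizes not disclosed to recruiters. Stratification by partial or total knee is optional.
- The list is prepared and held by someone outside recruitment, in sequentially numbered, opaque, sealed envelopes or in a REDCap-type module. The research coordinator should not hold it, because that role helps assess eligibility, takes consent and fits the device.
- Each assignment is released only after eligibility is confirmed and study consent is signed at the preoperative checkup.
- The sequence runs over consented patients, which removes the ambiguity between eligible and agreeing patients.

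The cost is one paragraph, a list with envelopes or a module, and a little time from a person outside recruitment. No extra patients or visits are needed. An incomplete last block may leave the arms a patient or two apart, and some guessing remains possible. Simple randomization would remove the guessing, but arm sizes would then vary around 15 with an SD of √(30 × 0.25) = 2.7.

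If alternation is kept, the study should be called quasi-randomized throughout, with a baseline-adjusted analysis and a log of every patient approached.
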